## **11.2 Audits and Inspections**

Authorized representatives of the Sponsor, a regulatory authority, or an IRB/EC may perform audits or inspections at the study center, including source data verification. The purpose of an audit or inspection is to systematically and independently examine all study-related activities and documents, to determine whether these activities were conducted, and data were recorded, analyzed, and accurately reported according to the protocol, ICH GCP, and applicable regulatory requirements. The Investigator will contact the Sponsor immediately if contacted by a regulatory agency about an inspection at the study center.

## **12.0 ETHICAL AND REGULATORY OBLIGATIONS**

### **12.1 Ethical Considerations**

The Investigator agrees to conduct this study in accordance with ethical principles that have their origin in the Declaration of Helsinki and are consistent with ICH GCP. The Investigator will conduct all aspects of this study in compliance with the protocol, ICH GCP and applicable regulatory requirements.

### **12.2 Informed Consent**

Before the start of required study procedures, the Investigator or his/her associate must obtain informed consent from each study participant (or the subject's legal representative) in accordance with ICH GCP, and country authority requirements. Separate Informed Consent Forms may be required for gene sequencing, and/or biomarker testing. Age appropriate assent and permission from a minor subject's parent or legal guardian is required for pediatric subjects. The subject or his/her legal representative must sign the current version of the written, IRB/EC-

approved Informed Consent Form in the presence of a witness and be given a copy. The Investigator will ensure that a copy of the signed consent is kept with the subject's records.

In accordance with ICH GCP and country authority requirements, an IRB/EC must review and approve this protocol and the Informed Consent Form prior to initiation of the study.

### **12.3      Ethics and Regulatory Review**

An IRB/EC should approve the final study protocol, including the final version of the Informed Consent Form, assent forms, parental permission forms and any other written information and/or materials to be provided to the subjects. The Investigator will ensure the distribution of these documents to the applicable IRB/EC, and to the study center staff.

The opinion of the IRB/EC should be given in writing. The Investigator should submit the written approval to Sponsor before enrollment of any subject into the study.

The IRB/EC should approve all advertising used to recruit subjects for the study.

The Sponsor should approve any modifications to the Informed Consent Form that are needed to meet local requirements.

If required by local regulations, the protocol should be re-approved by the IRB/EC annually.

Before enrollment of any subject into the study, the final study protocol, including the final version of the Informed Consent Form, is approved by the national regulatory authority or a notification to the national regulatory authority is done, according to local regulations.

The Sponsor will handle the distribution of any of these documents to the national regulatory authorities.

The Sponsor will provide regulatory authorities, IRB/ECs and Investigators with safety updates/reports according to local requirements.

Each Investigator is responsible for providing the IRB/EC with reports of any serious and unexpected adverse drug reactions from any other study conducted with the study drug. The Sponsor will provide this information to the Investigator so that he/she can meet these reporting requirements.

### **12.4      Subject Confidentiality**

The Investigator must ensure that the subject's confidentiality is maintained. On the eCRFs or other documents submitted to the Sponsor, subjects should be identified by their date of birth (month and year) and subject number only. Documents that are not for submission to the Sponsor (eg, signed Informed Consent Forms), should be kept in strict confidence by the Investigator.

In compliance with applicable regulations, it is required that the Investigator and institution permit authorized representatives of the Sponsor, the United States Food and Drug Administration (USFDA), other regulatory authorities, and the IRB/EC direct access to review the subject's original medical records for verification of study-related procedures and data. Direct access includes examining, analyzing, verifying, and reproducing any or all records and reports that are important to the evaluation of this study. The Investigator is obligated to inform and obtain the consent of the subject to permit named representatives to have access to the study-related records without violating the confidentiality of the subject.

### **13.0 STUDY ADMINISTRATION**

A coordinating Investigator for the PQ-110-001 study will be selected from the participating sites by the Sponsor.

#### **13.1 Investigator's Brochure**

Before the study begins, the Investigator will receive the QR-110 Investigator's Brochure (IB) describing all known contraindications, warnings, precautions, and adverse reactions associated with the administration of the study drug. If such information is revised while the study is in progress, the IB will be amended or revised and the Sponsor will provide the most current version to the Investigator.

#### **13.2 Protocol Amendments**

If there are any substantial changes to the study protocol, then these changes will be documented in a protocol amendment and in a new version of the protocol. Protocol amendments must be made only with the prior approval of the Sponsor. The Sponsor will inform the Investigator in writing of any amendment to the protocol. The Investigator must submit the protocol modifications and any Informed Consent Form modifications to the IRB/EC, and approval must be obtained before the modifications are implemented. The Investigator must send a copy of the approval letter from the IRB/EC to the Sponsor for review.

#### **13.3 Study Termination**

Both the Sponsor and the Investigator reserve the right to terminate the study according to the study contract. The Investigator should notify the IRB/EC in writing of the study's completion or early termination and send a copy of the notification to the Sponsor.

If the Sponsor, DMC, Sponsor Medical Monitor or designee, study center monitor, or appropriate regulatory officials discover conditions arising during the study that indicate that the study should be halted or that a study center should be terminated, this action may be taken after appropriate consultation. Termination may occur in accordance with the clauses contained in the study center's executed clinical study agreement. The Sponsor reserves the right to discontinue

the study prior to enrollment of the intended number of subjects, but intends only to exercise this right for valid scientific or administrative reasons.

If the clinical development of QR-110 is discontinued, the Sponsor shall immediately inform all Investigators/institutions and regulatory authorities. Study termination and follow-up will be performed in compliance with the conditions set forth in the ICH GCP guidelines ([ICH 2000](#)) and local regulatory requirements.

### **13.4 Study Documentation and Storage**

The Sponsor will provide the Investigator with records of drug shipments, eCRFs, and other forms as necessary. The Investigator and study staff are responsible for maintaining a comprehensive and centralized filing system of all study-related documentation, suitable for inspection at any time by representatives from the Sponsor and/or applicable regulatory authorities. Elements should include, but are not limited to:

- Subject files containing informed consents and supporting originals of source documentation.
- Study files containing the protocol with all amendments, IB, copies of pre-study documentation, and all correspondence to and from the IRB/EC, applicable country authorities, and the Sponsor.
- Records of drug accountability and all drug-related documentation.

In addition, all original source documents supporting entries in the eCRFs must be maintained and be readily available.

Upon the request of the Sponsor, designees, or the regulatory authorities, the Investigator will make all study records available for inspection, including subject dairies and source documents. This information will be treated as confidential.

No study document is to be destroyed without prior written agreement between Sponsor and the Investigator. Should the Investigator wish to assign the study records to another party or move them to another location, he/she must notify the Sponsor in writing of the new responsible person and/or the new location.

### **13.5 Use of Information**

All personal information pertaining to the subjects in this study and in any subsequent reports will be kept confidential. Subjects will be identified only by their month and year of birth and a subject number. It is the responsibility of the Investigator to keep a subject listing for cross-referencing.

The Investigator understands that the information developed in the clinical study will be used by the Sponsor in connection with the development of the study drug. This information may be disclosed to other clinical Investigators, to the US FDA, and to other government agencies.

### **13.6 End of Study and Final Report**

In North America, the Investigator or associate must notify the IRB/EC when the study is closed. If not initially provided by the Sponsor, a copy of the final study report must also be provided to Sponsor or its representative.

In the European Union, the Sponsor or its designee must notify the European Competent Authorities and ECs when the study is terminated, within 90 days of the last subject's completion of the study in the concerned country and/or worldwide in accordance with local requirements. In case of early termination, the deadline is 15 days. The Sponsor or its designee must provide a final report and/or synopsis to the European Competent Authorities and ECs at the latest 1 year after the study termination worldwide, in accordance with local requirements. A copy of this final report and associated synopsis must also be provided to the Investigator.

End of Study will be defined as the last visit for the last subject (LVLS) in the PQ-110-001 clinical study (Visit 21 or the End of Study Visit).

### **13.7 Financing and Insurance**

Financing and Insurance are addressed separately in the Clinical Study Agreement.

### **13.8 Publication Policy**

Publication policy is addressed separately in the Clinical Study Agreement.

## 15.0 APPENDICES

PLR	Pupillary Light Reflex
PP	Per Protocol
PT	Preferred Term
RTF	Rich Text Format
SAE	Serious Adverse Event
SAP	Statistical Analysis Plan
SD	Standard Deviation
SDC	Statistics and Data Corporation, Incorporated
SOC	System Organ Class
$T_{1/2}$	Half-Life
TEAE	Treatment-Emergent Adverse Event
VA	Visual Acuity
V_d	Apparent Volume of Distribution
VEP	Visual Evoked Potential
VFQ-25	25-Item Visual Functioning Questionnaire
WHO DDE	World Health Organization Drug Dictionary Enhanced
WOCBP	Women of Childbearing Potential

1. Introduction

The purpose of this statistical analysis plan (SAP) is to describe the planned analyses and reporting in support of protocol PQ-110-001, version 6.0 dated 02-Aug-2018.

This SAP is being written with due consideration of the recommendations outlined in the most recent International Council for Harmonisation (ICH) E9 Guideline entitled Guidance for Industry: Statistical Principles for Clinical Trials and the most recent ICH E3 Guideline, entitled Guidance for Industry: Structure and Content of Clinical Study Reports.

This SAP describes the data that will be analyzed and the subject characteristics, efficacy, and safety assessments that will be evaluated. This SAP provides details of the specific descriptive statistical methods that will be used.

In addition to this SAP, inferential analyses will be generated by [REDACTED] which will also be used to support the CSR. The descriptions of methods and statistical analyses used for these inferential analyses are described separately within the scope of the Cytel SAP of which a copy has been included in whole in [REDACTED] and which should be read in conjunction with this SAP.

The statistical analysis methods presented in this document will supersede the statistical analysis methods described in the clinical protocol. If additional analyses are required to supplement the planned analyses described in this SAP they may be completed and will be identified in the Clinical Study Report (CSR). Study Objectives

1.1 Primary Objective

The primary objective of the study is to evaluate the safety and tolerability of QR-110 administered via intravitreal (IVT) injection in subjects with Leber's Congenital Amaurosis (LCA) due to the *CEP290* p.Cys998X mutation.

1.2 Secondary Objectives

The secondary objectives of the study are:

- to evaluate the serum pharmacokinetics (PK) of QR-110 administered by IVT injection in subjects with LCA due to the *CEP290* p.Cys998X mutation
- to evaluate the efficacy of QR-110 administered by IVT injection in subjects with LCA due to the *CEP290* p.Cys998X mutation

1.3 Exploratory Objectives

1.4 Primary Endpoint

- Frequency and severity of ocular AEs in the treated and contralateral eyes

1.5 Secondary Endpoints

- Frequency and severity of non-ocular Adverse Events (AEs)
- Changes in ophthalmic examination findings
- Change from baseline in Best-Corrected Visual Acuity (BCVA) in treated eye and contralateral eye
- Change from baseline in near-infrared autofluorescence (NIRAF) data in treated eye and contralateral eye:
 - Horizontal diameter
 - Vertical diameter
 - Area
- Changes in SD-OCT findings in treated eye and contralateral eye with horizontal and vertical scan for:
 - Change from baseline in full retinal thickness (FRT) at foveal pit
 - Change from baseline in mean FRT (line scan)
 - Change from baseline in outer nuclear layer (ONL) thickness at foveal pit
 - Change from baseline in extent of ONL region
 - Change from baseline in photoreceptor outer segment thickness (OST) at foveal pit
 - Change from baseline in mean photoreceptor OST (line scan)
- Changes in safety parameters, including vital sign measurements, physical examination findings, electrocardiogram (ECG) and laboratory parameters
- Systemic exposure of QR-110 in serum
- Change from baseline in light sensitivity to red Full-field Stimulus Testing (FST) in treated eye and contralateral eye
- Change from baseline in light sensitivity to blue FST in treated and contralateral eye
- Change from baseline in white Pupillary Light Reflex (PLR) at 4 levels of illumination (ie, 4, 40, 400, and 4000 cd/m²) in treated eye and contralateral eye:
 - Pre-stimulus
 - Maximum amplitude
 - 0.9 seconds amplitude
- Overall latency (time to react)

1.6 Exploratory Endpoints

The study is not designed to have sufficient statistical power to assess efficacy of QR-110 in the treatment of LCA due to the *CEP290* p.Cys998X mutation. However, changes in clinical outcome measures associated with LCA due to the *CEP290* p.Cys998X mutation will be monitored over the course of the study.

2. Study Design and Procedures

2.1 General Study Design

The first-in-human study of QR-110 will be an open-label, multiple arm, multiple dose, dose escalation study to evaluate the safety and tolerability of QR-110 administered via IVT injection in subjects with LCA due to the *CEP290* p.Cys998X mutation. Subjects will be assigned to receive a specified dose level (loading dose and maintenance dose) of QR-110. No intrasubject dose escalation is planned. Up to 3 dose levels of QR-110 will be evaluated. Dose escalation decisions and initiation of dosing in pediatric subjects (6 to < 18 years of age) will be determined by the Data Monitoring Committee (DMC) and Sponsor Medical Monitor review of safety and tolerability data. The DMC and Sponsor Medical Monitor will also review all available safety data at key study time points (e.g., prior to the first subject in the first adult cohort (Cohort A1) receiving each subsequent dose of study drug).

QR-110 will be administered by unilateral IVT injection. Each subject will receive up to 4 doses of QR-110 in their worse eye (as defined by visual acuity at the Screening Visit, subsequently referred to as treatment eye) every 3 months and will be assessed for safety and tolerability at follow-up visits. The worst eye or treatment eye is defined in Section 8.1 of the SAP.

No placebo nor sham injections will be administered in the contralateral eye. The contralateral eye and the subject's own baseline measurements will serve as controls.

The DMC and/or Sponsor Medical Monitor may decide to de-escalate the dose, hold the dose (delay or skip), or discontinue study drug for an individual subject, in consultation with the Investigator. Subjects who discontinue study drug will continue to be followed for safety and efficacy.

An extension study is planned but is not within the scope of this SAP.

2.2 Dose Escalation and DMC Review

Specifics of the dose escalation plan are described in detail in Section 4.2.1.5 of the protocol.

Safety review, DMC review and stopping criteria are further detailed in protocol Section 4.2.2 and Section 4.2.4, and the DMC Charter. Otherwise, safety reviews will be conducted by the DMC and Sponsor Medical Monitor before each cohort initiation and on an ad hoc basis as needed. The Sponsor will also perform safety review on an ongoing basis.

2.3 Study Cohorts and DMC Review Schedules

QR-110 will be administered at up to 3 escalating dose levels and the study will include up to 6 cohorts (up to 3 adult cohorts and up to 3 pediatric cohorts). Each cohort will have at least 2 subjects and each dose level will be tested in 1 adult cohort and 1 pediatric cohort (Table 1). Dose escalation will proceed as described in Section 4.2.1.5 of the protocol. QR-110 will be administered via unilateral IVT injection

in the subject's worse eye (defined in Section 8.1 of the SAP) every 3 months and each subject will receive up to 4 doses of study drug.

While the protocol allows testing of up to 3 dose levels, no dose escalation to the highest dose was performed based on interim study results.

2.4 Study Visits

Study visits will be referred to in all tables and listings as the planned study day corresponding to the visit to enable reviewers to understand the assessment timing without referring to the protocol visit schedule shown in Table 1. Screening assessments may be repeated at a Re-Screening visit to reevaluate eligibility or safety parameters at the Investigator's discretion. In listings the re-screening visit will be "Unscheduled (Day -28 to -1)" and will only be used for further analyses if an average of all pre-dose measures is used for baseline. Dosing visits can occur over multiple days due to time constraints on subjects' schedules and visit procedures. Note that there is no Day 0 and that Day 1 corresponds to the day of first treatment. Any unscheduled visits outside of _____ will be noted as "Unscheduled" on tables and listings. The following table shows the scheduled visits, their planned study day and the acceptable visit windows for each scheduled visit. Scheduled visits that occur outside of the visit window will not be considered unscheduled visits, but will be presented and summarized as the scheduled visit.

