### **8.3      Laboratory Evaluations**

All laboratory evaluations will be conducted at a central laboratory, except Erythrocyte Sedimentation Rate (ESR), which will be conducted locally. Reference ranges for all laboratory parameters are provided in the Laboratory Manual.

Serum chemistries will include sodium, potassium, chloride, bicarbonate (or serum carbon dioxide), blood urea nitrogen (BUN), creatinine, glucose, calcium, phosphorus, ALT, AST, gamma-glutamyl transferase (GGT), alkaline phosphatase, total bilirubin, uric acid, lactic dehydrogenase (LDH), albumin, total protein, triglycerides, and cholesterol. Estimated Glomerular Filtration Rate (eGFR) is to be calculated using the Chronic Kidney Disease Epidemiology Collaboration (CKD-EPI) Creatinine Equation 2009 calculation for adult subjects and Schwartz equation, according to the recommendation from National Institutes of Health/National Institute of Diabetes and Digestive and Kidney Diseases (NIH/[NIDDK](#)), for pediatric subjects.

Hematology will include a complete blood count (CBC): CBC with absolute differential (hematocrit, hemoglobin, white blood count, red blood cell count, neutrophils, granulocytes, lymphocytes, monocytes, eosinophils, basophils, platelet count). Urinalysis (by visual inspection and dipstick) will include color and appearance, specific gravity, pH, protein, glucose, blood, ketones, bilirubin, leukocyte, nitrite, and urobilinogen. In addition, microscopic analyses will be performed on samples with abnormal dipstick results.

C4, Hemolytic complement 50 (CH50), INR, ESR and C Reactive Protein (CRP) will also be assessed.

For female subjects of child bearing potential, a serum pregnancy test is required at Screening. Urine pregnancy tests are acceptable for subsequent time points.

Subject eligibility is determined based on Screening laboratory values. If any relevant changes in the subject's medical history occur between Screening and Day 1, the Investigator should repeat laboratory assessments prior to the subject's first dose of study drug to confirm eligibility.

Repeat laboratory tests are permitted to confirm potentially spurious values or false positive results, at the discretion of the Investigator. Repeat analysis results for any laboratory assessments that are eligibility criteria should be discussed with the Sponsor Medical Monitor prior to subject inclusion.

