7.2.1 MISSING MOBILITY COURSE COMPOSITE SCORE IMPUTATIONS FOR CENTRAL READING CENTER GRADING

7.3 Definition of Baseline

Baseline is defined as the last measurement prior to the first dose of study drug in the treated eye for IOP, laboratory parameters, and the safety endpoints slit lamp biomicroscopy, posterior segment/fundus exam, vital signs, and ECG . For ophthalmic parameters BCVA, FST, mobility course, OCI and PLR measured at Screening and Visit 2 (Day 1) the average will be defined as baseline. For other ophthalmic parameters, NIRAF, SD-OCT, and ERG, planned to be done once at baseline, the average will be defined as baseline if the exam is repeated. Change from baseline will be calculated as follow-up visit/time point minus baseline visit/time point.

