12.4 Intraocular Pressure (IOP)

Intraocular pressure (IOP) will be assessed by tonometry (Goldmann Applanation Tonometer, Tono-pen, Noncontact Tonometer [puff tonometry], or Icare Tonometer [rebound tonometry]) according to the optical exam schedule of Section 3.5 of the SAP. Results will be taken from a single measurement per eye and will be recorded in mmHg.

The IOP values and changes from baseline for each eye (treated eye and contralateral eye) will be summarized using continuous descriptive statistics by visit and eye for each dose group and for all subjects. Baseline IOP is the last measurement prior to the first dose of study drug in the treated eye and may occur on a different date than dosing. The first measure taken immediately post-dose will be included in a change from baseline analysis. A subject listing of IOP will also be produced include IOP related AESIs. Tables will also include AESI for each visit with counts and percentages for each dose

group and cohort with the definition for the IOP related AESI according to Section 13.1.1 of the SAP. IOP related AESI will include those TEAEs with MedDRA PT of 'intraocular pressure increased'. In order to establish if results at individual visits resulted in an AESI report or not, the onset date of each reported AESI related to IOP will be compared to dates of IOP assessments, and assessments with dates between the onset date and resolution of the corresponding AESI will be flagged as having led to an AESI report.

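### SAP 2.4 keeps re-screening values out of the safety baselines that SAP 7.3 sets as the last measurement before first dose

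*SAP*

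**What the plan says.** SAP 2.4 (Study Visits) describes the visit's purpose: "Screening assessments may be repeated at a Re-Screening visit to reevaluate eligibility or safety parameters". It gives the visit an unscheduled pre-dose label in listings and limits its use in analysis: "and will only be used for further analyses if an average of all pre-dose measures is used for baseline".

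SAP 7.3 (Definition of Baseline) has two kinds of rule.

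- **Last value.** "Baseline is defined as the last measurement prior to the first dose of study drug in the treated eye for IOP, laboratory parameters". The same sentence puts the slit-lamp and fundus examinations, vital signs and ECG under this rule. It makes no exception for re-screening or unscheduled values.
- **Average.** For BCVA, FST, mobility course, OCI and PLR "measured at Screening and Visit 2 (Day 1) the average will be defined as baseline". NIRAF, SD-OCT and ERG are averaged if repeated.

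SAP 12.4 restates the last-value rule for IOP and adds that the measurement is valid "and may occur on a different date than dosing". Protocol 10.4 defines baseline as the most recent pre-dose data and/or the average.

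On laboratory tests, protocol 8.3 says: "Subject eligibility is determined based on Screening laboratory values". It also says: "Repeat laboratory tests are permitted to confirm potentially spurious values or false positive results, at the discretion of the Investigator". Repeat results on eligibility tests are to be discussed with the Sponsor Medical Monitor before the subject is included. Protocol 8.5 allows repeat ECGs for the same kind of reason.

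**The concern.** One stated purpose of re-screening is to look again at safety parameters. Those parameters have last-value baselines, so they are the ones for which SAP 2.4 bars the re-screening result from analysis. Where that result is the last one before dosing, 7.3 makes it the baseline and 2.4 forbids it. Neither section refers to the other, so two programmers could derive different baselines and each be following the SAP.

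If 2.4 is followed, the baseline is the earlier value, and that may be the one the repeat was meant to check. A falsely high baseline hides a later rise of the same size and turns a normal later value into an apparent fall. What is at stake is the descriptive change-from-baseline summaries of laboratory, ECG and vital-sign data, which belong to a secondary endpoint under the safety objective.

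**Working it through.** The plan gives no figure on this point, so there is none to reproduce. The check compares the rules and then sizes the effect of one wrong baseline.

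**1. Which baseline each rule gives for a last-value parameter**

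| Pre-dose values available | SAP 7.3 | SAP 2.4 followed literally | Conflict? |
|---|---|---|---|
| Screening only | Screening | Screening | No |
| Screening, re-screening, Day 1 pre-dose | Day 1 | Day 1 | No |
| Screening, re-screening, no Day 1 pre-dose | Re-screening | Screening | **Yes** |

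For averaged parameters 2.4 admits the re-screening value, so there is no conflict.

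**2. Where the third row can arise**

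- *IOP, slit lamp, fundus:* unlikely. Protocol 8.8 has ophthalmic examinations at all study visits, so a Visit 2 value should exist, provided that examination precedes the injection.
- *Laboratory tests:* most plausible. Eligibility rests on Screening values. Protocol 8.3 calls for a pre-dose repeat only after a relevant change in medical history, and protocol 8.12 does not list laboratory tests among the measures taken at both Screening and Day 1.
- *ECG and vital signs:* possible. The list in protocol 8.12 does not name them either.
- *All parameters:* protocol 4.2.1.1 mentions a second pre-dose set on Day 1 according to the schedule of events. That schedule is not in the text available, so the frequency cannot be determined.

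**3. Size when it arises**

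Let b be the value 7.3 would use, b + e the earlier value kept under 2.4, and y any later value.

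- Change under 7.3: y - b
- Change under 2.4: y - (b + e) = (y - b) - e

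The subject's change is off by -e at every post-baseline visit. One such subject among n moves the mean change by -e/n:

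- n = 2 (minimum cohort size, SAP 2.3): -e/2
- n = 11 (all subjects at interim analysis 2, SAP 7.6): -e/11

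**4. Illustration (assumed values)**

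ALT is 1.5 x ULN at Screening, above the 1.2 x ULN limit in exclusion criterion 8. It is 0.9 x ULN at re-screening and 1.5 x ULN on treatment. There is no Day 1 sample.

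- e = 1.5 - 0.9 = 0.6 x ULN
- Change under 7.3: 1.5 - 0.9 = +0.6 x ULN
- Change under 2.4: 1.5 - 1.5 = 0
- Shift in mean change, cohort of 2: -0.6/2 = -0.30 x ULN
- Shift in mean change, 11 subjects: -0.6/11 = -0.055 x ULN

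**The case against.** The best reply is that the SAP already shows which rule governs. SAP 15.2 says baseline is measurement-specific under the SAP's baseline section (cited there as 8.3, printed as 7.3). SAP 12.4 and protocol 10.4 agree with it. SAP 2.4 is mainly about visit labels, and a programmer would normally go to 7.3 for the baseline flag. This stands as evidence of intent. It does not remove the conflict, because 2.4 goes beyond labelling and states a rule on use in analysis.

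Several stronger readings are tempting but not supported.

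- *Every last-value baseline is affected.* It is not: any Day 1 pre-dose value removes the conflict. The medical-history sentence in protocol 8.3 concerns eligibility and does not show that no Day 1 sample is drawn.
- *Every repeat test is discarded.* SAP 2.4 restricts only the re-screening visit. Protocol 8.3 and 8.5 do not call their repeats by that name, so the rule applies only when the repeat is done there. Nor does 2.4 bar other unscheduled pre-dose values.
- *A spurious baseline did occur.* No document shows that any subject was re-screened. An out-of-range laboratory value may also be accepted with Medical Monitor concurrence, without a repeat.
- *The main safety result is compromised.* The primary endpoint is ocular adverse events, which does not use this baseline. Laboratory adverse events depend on clinical significance, not on the derived change.
- *Shift tables are distorted.* Laboratory shift tables appear in protocol 10.6.3 but not in SAP 12.8, and the SAP says its methods supersede the protocol's.

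Subject listings also show all values, so with 11 subjects a careful reader could find both. That limits the harm but leaves the summary tables wrong.

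**Conclusion.** The concern holds in limited form. SAP 2.4 contradicts SAP 7.3, and also SAP 12.4 and protocol 10.4, on whether a re-screening value can be the baseline for the six last-value safety parameters. Section 2.4 is the outlier. Followed literally, it can give a wrong baseline.

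The size is an error of -e in one subject's change at every later visit, hence -e/2 in the mean of a cohort of 2 or -e/11 over 11 subjects. This assumes one affected subject, a re-screening value that is the last before dosing, no Day 1 pre-dose value after it, and an earlier value that is wrong by e. How often these conditions meet cannot be told from the documents. The effect is confined to descriptive safety summaries. The averaged efficacy and imaging endpoints and the primary endpoint are untouched. The correction is worth making because the error can hide a rise in a first-in-human study and costs almost nothing to remove.

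**What to change.** Amend SAP 2.4 to say that re-screening values are eligible for baseline under SAP 7.3: as the last pre-dose measurement for IOP, laboratory parameters, slit lamp, fundus, vital signs and ECG, and as part of the average for the averaged parameters. Keep the unscheduled pre-dose label for listings only. No further validity standard for the last value is needed, since 7.3 contains none.

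The cost is one sentence in the SAP and one baseline-flag derivation, with no new data. Checking which treated subjects, if any, have a re-screening value and no Day 1 pre-dose value would show whether any table changes.
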